17.3. Written Informed Consent

The Investigator (or authorized designee) at each center will ensure that the subject and parent/caregiver (as per local requirements or the subject's legal representative) is given full and adequate oral and written information about the nature, purpose, potential and possible risks and benefits of the study. Each prospective subject and parent/caregiver (as per local requirements) will receive an IRB-approved ICF that summarizes the pertinent study information and will be given ample time to read the form and ask questions about the study. All information is to be provided in a language understandable to the subject and must not include any language that waives the subject's legal rights. Prospective subjects must also be informed of their right to withdraw consent without prejudice at any time during the study. If the subject chooses to participate, he/she must sign the ICF/assent form (as per local requirements) and if required, the parent/caregiver must sign the parent/caregiver ICF before any study-specific procedures are conducted.

All subjects will be informed of their rights to privacy and will be made aware that the study data will be submitted to Alkermes, the IRB, the contract research organization (CRO), if applicable, and to regulatory authorities for review and evaluation for the duration of the study and until the project has been approved for marketing, or is withdrawn from investigation. They will also be informed that the study monitor may inspect their medical records to verify the accuracy and completeness of the study records and results.

Significant changes to the protocol or product safety information may require a revision of the ICF/assent form, which must be reviewed and approved by the IRB, and then signed by all applicable study participants.

The time that informed consent is obtained must be documented. The Investigator must maintain the original, signed ICF/assent form in the subject's source documents. A copy of the signed ICF/assent form must be given to the subject.

18. DATA HANDLING AND RECORDKEEPING

An overview of study data handling and recordkeeping procedures and restrictions is provided in the subsequent sections; please refer to the CSA for further details.

18.1. Data Capture

As stated in Section 16.1, this study will use eCRFs for capturing data. All entries, corrections, and alterations will be made by the Investigator or other authorized study personnel. All data entries will be verified for accuracy and correctness by independent monitors. The electronic data capture system maintains a full audit trail.

A paper copy of all laboratory reports will remain with the source documents at the study site. All electronic source data collected outside of the eCRF, such as e-diaries, central laboratory, or central MRI data, will be transferred directly to EDC or directly to Alkermes for incorporation into the final datasets. All out-of-range laboratory values will be deemed as clinically significant or not clinically significant by the Investigator. Clinically significant values will be considered AEs and will be recorded as such on the eCRFs.

All AEs will be coded using MedDRA. Concomitant medications will be categorized using the WHO-ATC classification system.

18.2. Inspection of Records

Alkermes or its representative will be allowed to conduct site visits to the investigational facilities for the purpose of monitoring any aspect of the study. The Investigator agrees to allow the monitor to inspect the drug storage area, study drug stocks, drug accountability records, subject charts and source documents, and other records relative to study conduct.

18.3. Retention of Records

Retention and storage of all essential clinical study documents shall be governed by the terms and conditions of the site's CSA and in accordance with ICH guidelines/local regulatory requirements as follows:

Essential documents should be retained until at least 2 years after the last approval of a marketing application in an ICH region and until there are no pending or contemplated marketing applications in an ICH region, or at least 2 years have elapsed since the formal discontinuation of clinical development of the investigational product. These documents should be retained for a longer period, however, if required by the applicable regulatory requirements or by the terms of the CSA. It is the responsibility of the Sponsor to inform the Investigator/Institution as to when these documents no longer need to be retained.

Subjects' medical files should be retained in accordance with the applicable legislation and in accordance with the maximum period of time permitted by the hospital, institution, or private practice.

18.4. Use of Information and Publication Policy

Data generated in this study are proprietary information that are the sole property of Alkermes. Results of the study are to be held in confidence by both the Investigators and the Sponsor.

Please refer to the CSA for details on the procedures for publishing and presenting data.

20. APPENDIX A: PARTIAL LIST OF PROHIBITED CYTOCHROME P450 (CYP) 3A INHIBITORS AND INDUCERS

The following is a list of CYP3A inhibitors and inducers that subjects are to avoid within 30 days of enrollment and through follow-up. This list is not comprehensive.

Table 6: Partial List of CYP3A Inhibitors and Inducers

| Moderate-to-S | Strong Inhibitors | Moderate-to-Strong Inducers |
|-------------------------------------|---|-----------------------------|
| Aprepitant | Idelalisib | Avasimibe |
| Boceprevir | Indinavir/Ritonavir ^a | Bosentan |
| Cimetidine | Itraconazole | Carbamazepine |
| Ciprofloxacin | Ketoconazole | Efavirenz |
| Clarithromycin | Lopinavir/Ritonavir ^a | Enzalutamide |
| Clotrimazole | Mibefradil | Etravirine |
| Cobicistat | Nefazodone | Mitotane |
| Conivaptan | Nelfinavir | Modafinil |
| Crizotinib | Paritaprevir/Ritonavir and (Ombitasvir and/or Dasabuvir) ^a | Phenobarbital |
| Cyclosporine | Posaconazole | Phenytoin |
| Danoprevir/Ritonavir ^a | Ritonavir ^a | Rifabutin |
| Diltiazem | Saquinavir/Ritonavir ^a | Rifampin |
| Dronedarone | Telaprevir | St. John's Wort |
| Elvitegravir/Ritonavir ^a | Telithromycin | _ |
| Erythromycin | Tipranavir/Ritonavir ^a | _ |
| Fluconazole | Tofisopam | _ |
| Fluvoxamine | Troleandomycin | _ |
| Grapefruit Juice | Verapamil | _ |
| Imatinib | Voriconazole | _ |

^a Ritonavir is usually given in combination with other anti-HIV or anti-HCV drugs in clinical practice. Caution should be used when extrapolating the observed effect of ritonavir alone to the effect of combination regimens on CYP3A activities

Source: (Food and Drug Administration 2016; University of Washington: School of Pharmacy 2017a; University of Washington: School of Pharmacy 2017b)

21. APPENDIX B: PARTIAL LIST OF CYP1A2 MODERATE-TO-STRONG INHIBITORS AND MODERATE INDUCERS

Table 7: Partial List of CYP1A2 Inhibitors and Inducers

| Moderate-to-Strong | CYP1A2 Inhibitors | Moderate CYP1A2 Inducers |
|----------------------------|---------------------|--------------------------|
| Ciprofloxacin ^a | Oral Contraceptives | Phenytoin ^a |
| Enoxacin | Zafirlukast | Rifampin ^a |
| Fluvoxamine ^a | _ | Ritonavir ^a |
| Methoxsalen | _ | Teriflunomide |
| Mexiletine | _ | Tobacco |

^a These drugs are also known to be CYP3A inhibitors or inducers and are prohibited, as shown in Appendix A Source: (Food and Drug Administration 2016)

22. APPENDIX C: PARTIAL LIST OF MEDICATIONS KNOWN TO BE ASSOCIATED WITH PROLONGED QTc INTERVAL AND TORSADE DE POINTES

The following is a list of medications known to be associated with torsade de pointes. This list is not comprehensive.

Table 8: Partial List of Medications Known to Be Associated with Prolonged QTc Interval and Torsade de Pointes

| Generic Name | | | | |
|-----------------------------|---------------------------|---------------------------------|--|--|
| Amiodarone | Domperidone | Oxaliplatin | | |
| Anagrelide | Donepezil | Papaverine HCL (Intra-coronary) | | |
| Arsenic trioxide | Dronedarone ^a | Pentamidine | | |
| Azithromycin | Droperidol ^b | Pimozide ^b | | |
| Chloroquine | Erythromycin ^a | Procainamide | | |
| Chlorpromazine ^b | Escitalopram | Propofol | | |
| Cilostazol | Flecainide | Quinidine | | |
| Ciprofloxacin ^a | Fluconazole ^a | Sevoflurane | | |
| Citalopram | Haloperidol ^b | Sotalol | | |
| Clarithromycin ^a | Ibutilide | Thioridazine ^b | | |
| Cocaine ^b | Levofloxacin | Vandetanib | | |
| Disopyramide | Methadone ^b | _ | | |
| Dofetilide | Ondansetron | _ | | |

^a These drugs are also known to be CYP3A inhibitors or inducers and are prohibited, as shown in Appendix A

^b Antipsychotics (other than the study drug), drugs of abuse, and prescribed opioids are prohibited in the study

SD	Standard deviation
SMQ	Standardized MedDRA queries
SOC	System organ class
TEAE	Treatment-emergent adverse event
ULN	Upper limit of normal
WHO	World Health Organization

1. INTRODUCTION

This statistical analysis plan (SAP) describes the statistical methods to be used for analyses and presentation of safety and efficacy data for study ALK3831-A308 to support the clinical study report (CSR) development. This document has been prepared based on Alkermes [ALKS 3831-A308 Study Protocol Amendment 3.0](#) (dated 09 May 2019) and Alkermes [ALKS 3831-A308 Interim Statistical Analysis Plan to Support New Drug Application \(NDA\) Submission](#) (dated 09 Jun 2019).

Subjects who have completed or prematurely discontinued ALKS 3831 will be included in the analysis described in this document.

1.1. Study Objectives

1.1.1. Primary Objective

The primary objective of this study is to evaluate the long-term safety, tolerability, and durability of treatment effect of ALKS 3831 in subjects with schizophrenia, schizophreriform disorder, or bipolar I disorder.

[figure not shown]
1.2. Summary of the Study Design

Subjects are eligible to be enrolled in the study within 7 days after completing the antecedent studies (ALK3831-A304, ALK3831-A306, or ALK3831-A307).

Subjects enrolled in the study will be started on the same olanzapine dose that they had maintained at the end of the antecedent study. Available doses of ALKS 3831 will be 5, 10, 15, and 20 mg olanzapine combined with 10 mg samidorphan (henceforth to be referred to as 5/10, 10/10, 15/10, and 20/10 mg). Subjects may be titrated to a different dose after the start of the study at the Investigator's discretion. Dosing will be flexible throughout the study; however, frequent adjustments are discouraged. Dose adjustments will only be performed on-site at the study center. Subjects requiring dose adjustments between scheduled visits will need to arrange an unscheduled visit.

Safety assessments will include adverse event (AE) monitoring, clinical laboratory testing, vital signs, body weight and the Columbia-Suicide Severity Rating Scale (C-SSRS). Psychiatric symptoms will be evaluated using the Clinical Global Impressions-Severity (CGI-S) scale. Additional assessments will include Impact of Weight on Quality of Life-Lite Questionnaire (IWQOL-Lite).

A schematic of the study design is provided in [Figure 1](#).

Figure 1: Study Design Schematic

^aVisits will occur monthly throughout the 48-month Treatment period. Subjects will start the study on the equivalent olanzapine dose to what they maintained at the end of the antecedent study. The dose may be adjusted to either 5/10, 10/10, 15/10, or 20/10mg throughout the study period based on investigator discretion, and such dose adjustments will require subjects to visit the study site.

2. SAMPLE SIZE CONSIDERATION

No formal sample size calculation is performed for this extension study. A sample size of approximately 500 is based on the estimated maximum number of subjects who might be expected to continue from the antecedent Phase 3 studies within 7 days (ALK3831-A304, ALK3831-A306, or ALK3831-A307).

3. DATA ANALYSIS**3.1. General Statistical Methodology**

Baseline for efficacy or safety analyses is defined as the last non-missing assessment before the first dose of ALKS 3831 in the ALK3831-A308 study, and it will be used for all efficacy and safety analyses, unless specified otherwise.

All results from this analysis will be presented for the overall group, ie all subjects as a single group, and not by previous treatment sequence in antecedent studies of ALK3831-A303 and ALK3831-A305.

In general, descriptive statistics: n, mean, standard deviation (SD), median, minimum, and maximum, for continuous variables and number and percentage of subjects in each category for categorical variables will be provided.

All source data will be presented as subject data listings.

3.2. Definitions of Analysis Populations**3.2.1. Safety Population**

The Safety Population will include all subjects who enrolled and received at least one dose of ALKS 3831 in the ALK3831-A308 study. All analyses will be conducted using the Safety Population except for AEs in the safety follow-up period and AE to evaluate the potential for

drug withdrawal and dependence. The populations used for the analyses of these events are specified below.

3.2.2. Follow-up Safety Population

Follow-up Safety Population will be defined as subjects in the Safety Population and met any of the following criteria:

- Completed at least one follow-up visit after >7 days of the last dose of ALKS 3831
- Reported at least one AE after >7 days of the last dose of ALKS 3831
- Follow-up Safety Population will be used to analyze the AEs in the safety follow-up period

3.2.3. Post-discontinuation Safety Population

Post-discontinuation Safety Population will be defined as subjects in the Safety Population and met any of the following criteria:

- Completed at least one follow-up visit >2 days after the last dose of ALKS 3831
- Reported at least one AE >2 days after the last dose of ALKS 3831

AEs to evaluate potential for drug withdrawal and dependence emerging following discontinuation of ALKS 3831 will be assessed for this population, during the period of >2 days to 16 days after the last dose of drug for subjects with at least 4 weeks ALKS 3831 exposure.

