7.3. Subject Withdrawal

A subject may be discontinued from the study at any time if the subject, Investigator, or Sponsor determines that it is not in the best interest of the subject to continue participation. If a subject has an absolute neutrophil count (ANC) $< 1.0 \times 10^3$ per μ L or Hemoglobin A1c (HbA1c) $\ge 6.5\%$ at any time, the PI (or designee) should discontinue the subject from participation immediately. Reasons for discontinuation include:

- Adverse Event
- Lack of Efficacy
- Lost to Follow-up
- Withdrawal by Subject
- Protocol Deviation (including non-compliance with study drug or study procedures)
- Pregnancy
- Study Terminated by Sponsor
- Other

If a subject withdraws from the study for any reason, any ongoing AEs will be followed until resolution, until deemed stable by the Investigator, or until the subject is deemed by the Investigator to be lost to follow-up. If, in the opinion of the Investigator, it is necessary to monitor a subject beyond the safety follow-up visit, the follow-up period may be extended as necessary. In such instances, the Sponsor and Investigator will agree to an acceptable follow-up schedule.

In the event that a subject chooses to withdraw from the study, the Investigator should make a reasonable effort to ascertain the reason(s) for withdrawal, while fully respecting the subject's rights. Subjects who terminate the treatment early (prior to Visit 25) will complete an early termination (ET) visit and the 4-week Safety Follow-up period. The ET visit should be scheduled as close as possible to the subject's last dose and will mimic the assessments scheduled to be conducted at the EOT Visit. If the subject fails or refuses to return to the study center, an attempt must be made to contact the subject by telephone in order to assess as many safety and efficacy parameters as possible. All data collected over the telephone must be documented and kept in the subject's record.

The Investigator must maintain a record of all subjects who fail to complete the study. The reason for study discontinuation will be documented and made on the appropriate electronic case report form (eCRF). If a subject is lost to follow-up, a reasonable attempt to contact the subject must be made and documented.

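### SAP 3.2.2, and less directly 3.2.3, let a subject without a follow-up visit into the denominator only if an AE was reported, so the post-treatment percentages depend on the outcome

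*SAP*

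**What the plan says.** SAP 3.2.1 uses the Safety Population for everything except AEs in the safety follow-up period and AEs bearing on withdrawal and dependence. Those go to two other populations.

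- **SAP 3.2.2, Follow-up Safety Population.** Either of two criteria is enough: "Completed at least one follow-up visit after >7 days of the last dose of ALKS 3831" or "Reported at least one AE after >7 days of the last dose of ALKS 3831". Its purpose: "Follow-up Safety Population will be used to analyze the AEs in the safety follow-up period". SAP 3.8.1 reports these AEs as number and percentage of subjects, by system organ class and preferred term.
- **SAP 3.2.3, Post-discontinuation Safety Population.** The link is again either/or: "Post-discontinuation Safety Population will be defined as subjects in the Safety Population and met any of the following criteria". The criteria are "Completed at least one follow-up visit >2 days after the last dose of ALKS 3831" and "Reported at least one AE >2 days after the last dose of ALKS 3831". Withdrawal and dependence AEs are then assessed "during the period of >2 days to 16 days after the last dose of drug for subjects with at least 4 weeks ALKS 3831 exposure". This section does not say that a percentage will be given.

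No analysis with another denominator is planned, and the disposition summary in SAP 3.3 does not count subjects without a follow-up visit.

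Protocol 7.3 expects early terminators to complete a termination visit and the 4-week follow-up. It also foresees subjects who do not come back, for whom "an attempt must be made to contact the subject by telephone in order to assess as many safety and efficacy parameters as possible".

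**The concern.** A subject who never attends follow-up enters the denominator if an AE is on record and stays out if none is. Each AE-only entrant adds one to both numerator and denominator of the any-AE row in 3.2.2. An AE-free non-attender adds nothing to either. The percentage then mixes the risk of an AE with attendance and with how completely AEs of non-attenders reach the database.

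At stake is how the AE figures after stopping are read, including those meant to inform withdrawal and dependence. The study has one arm and its analyses are descriptive, so these figures will be taken at face value or set beside other studies with different attendance. The planned tables do not give a reader the counts needed to undo the selection.

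**Working it through.** The plan gives no attendance rate, AE rate or percentage, so there is no figure to reproduce. What follows is algebra with assumed inputs.

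**Notation**
- a = proportion with a follow-up visit past the cut-off (assumed 70-90%)
- p = proportion with an AE past the cut-off, taken as equal in attenders and non-attenders (assumed 10%)
- c = share of non-attenders' AEs that get reported (assumed 100% or 20%)

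**1. Any-AE row, SAP 3.2.2**

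AE-only entrants, as a share of all subjects, are (1 − a)pc. All of them are cases. So

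SAP percentage = [ap + (1 − a)pc] / [a + (1 − a)pc], against a visit-only rate of p.

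| a | c = 100% | c = 20% |
|---|---|---|
| 90% | 0.100/0.910 = 11.0% | 0.092/0.902 = 10.2% |
| 80% | 0.100/0.820 = 12.2% | 0.084/0.804 = 10.4% |
| 70% | 0.100/0.730 = 13.7% | 0.076/0.706 = 10.8% |
| 100% | 10.0% | 10.0% |

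The relative increase over the visit-only rate is about 10-37% with full reporting and about 2-8% with 20% reporting.

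**2. A single row, SAP 3.2.3**

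Entry is by any AE more than 2 days after the last dose, with any preferred term and no upper day limit. The outcome is narrower: withdrawal or dependence terms on days >2 to 16. For V attenders and e AE-only entrants, with target-AE proportions t_V and t_e,

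SAP value = (V·t_V + e·t_e) / (V + e).

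This weighted average exceeds t_V only if t_e exceeds t_V. As an illustration take 500 subjects (the approximate planned number), any AE 10%, target AE 3% and full reporting:

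| a | V | e | Same AE mix (t_e = 3/10 = 30%) | No target AE in entrants (t_e = 0) |
|---|---|---|---|---|
| 90% | 450 | 5 | (13.5 + 1.5)/455 = 3.30% | 13.5/455 = 2.97% |
| 80% | 400 | 10 | (12 + 3)/410 = 3.66% | 12/410 = 2.93% |
| 70% | 350 | 15 | (10.5 + 4.5)/365 = 4.11% | 10.5/365 = 2.88% |

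The visit-only value is 3.00% throughout, so the row can move either way. The same formula governs individual preferred-term rows in 3.2.2; only the any-AE row has t_e = 100% by construction.

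**3. Against true incidence**

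Let non-attenders have more AEs, mostly unreported: 500 subjects, 70% attendance, 10% in attenders, 30% in non-attenders, 30% of the latter reported.
- SAP: (35 + 13.5)/(350 + 13.5) = 48.5/363.5 = 13.3%
- True: (35 + 45)/500 = 16.0%

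The SAP figure is then above the visit-only 10% but below the truth.

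**4. All stopped subjects as denominator, same numerator**

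With p = 10% and a = 70%: (35 + 15)/500 = 10.0% with full reporting and (35 + 3)/500 = 7.6% with 20% reporting. Unreported AEs count as none, so this can only be at or below the true rate.

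**The case against.** The strongest reply is that little may turn on this. Protocol Table 3 schedules a safety follow-up visit for everyone, and with full attendance the effect vanishes. Scheduled AE collection runs to that visit (Protocol 13.5), so full reporting from those who missed it is an extreme case; at 20% reporting the shift is below one percentage point. The tables are descriptive and source data are listed. All of this stands and limits the size. It does not make the denominator independent of the outcome.

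Three stronger readings are tempting, and the documents do not support them.

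- **Every non-attender in both populations is a case.** This is true only of the any-AE row in 3.2.2. In 3.2.3 a subject admitted by an unrelated or later AE enlarges the denominator alone. That section also promises no percentage.
- **The percentages are overstated by some 10-40%.** That range needs full reporting and 70-90% attendance, its upper end also needs an AE rate nearer 5% than 10%, and it is relative to a visit-only rate. Against true incidence the sign itself is open.
- **The rule discards AE-free subjects reached by the telephone call the protocol requires.** Protocol 7.3 requires an attempt. The sentence follows the text on the termination visit, which is to fall close to the last dose, so a call may precede either cut-off. The SAP does not define a follow-up visit, so the handling of a later call is not settled. The protocol places telephone data in the subject's record and does not say that AE-free calls reach the database.

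Nor does samidorphan's Schedule II status add weight: the protocol attributes it to chemical structure and opium-alkaloid origin, and the compound is an opioid antagonist.

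**Conclusion.** The point holds in limited form. Followed as written, SAP 3.2.2 and 3.2.3 give denominators that depend on whether an AE was reported. For the any-AE row of 3.2.2 the figure exceeds the visit-only rate whenever an AE-only entrant exists and not every attender is a case. For withdrawal and dependence rows in 3.2.3 the direction depends on the AE mix: upward if it matches that of attenders, slightly downward if AE-only entrants have no target AE in the window.

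The size cannot be fixed from the documents. The shift in the any-AE row from 10% to between 10.2% and 13.7% rests on assumed values for the AE rate, attendance and reporting, and on equal risk in attenders and non-attenders. This is a definitional flaw in descriptive safety tables, worth correcting because the repair is cheap.

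**What to change.** 1. In SAP 3.2.2 and 3.2.3, define the percentage denominator without reference to AEs: Safety Population subjects with a follow-up visit more than 7 days (3.2.2) or more than 2 days (3.2.3) after the last dose. For 3.2.3 keep the existing minimum-exposure condition. If contacts at which AEs were assessed are in the database with dates, include those past the cut-off, whether or not an AE was found.
2. Tabulate or list separately the AEs of subjects who would have entered by AE alone, so that no event is lost.
3. State the number of subjects with no follow-up visit past each cut-off.
4. As a sensitivity analysis, give the rate over all Safety Population subjects who stopped dosing, with all reported events in the numerator. Label it a lower bound, because unobserved subjects count as AE-free.
5. State in 3.2.3 whether percentages will be reported.

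The cost is a few lines of SAP text, one extra column or listing, and slightly lower headline percentages. Study conduct does not change. The visit-based denominator needs only visit and last-dose dates that the SAP's present definitions already use. The contact-based extension depends on data that may not have been captured: the SAP was approved in December 2023, after the targeted completion in the fourth quarter of 2022, so it should stay conditional.
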